### **14.3 Confidentiality**

Attention is drawn to the regulations promulgated by the ICH E6 GCP guidelines, local confidentiality requirements and the FDA under the Freedom of Information Act providing, in part, that information furnished to clinical Investigators and IRBs/IECs will be kept confidential by the FDA/EMA and local regulatory agencies only if maintained in confidence by the clinical Investigator and IRB/IEC. The Sponsor will comply with the applicable regulations that ensure

the security and privacy of the individually identifiable health information of the study subjects is maintained and the rights of the subjects are protected. By signing this protocol, the Investigator affirms to the Sponsor that the Investigator will maintain, in confidence, information furnished to him/her by the Sponsor and will divulge such information to the IRB/IEC under an appropriate understanding of confidentiality with such board.

## 15.0 PUBLICATION POLICY

All data are the property of the Sponsor. However, it is intended that the results of the study will be published and/or presented at scientific meetings. Any formal presentation or publication of data from this trial will be considered as a joint publication by the Investigator(s) and appropriate Sponsor personnel. Authorship will be determined by mutual agreement.

The Sponsor must receive copies of any intended communication in advance of publication (at least 14 days for an abstract or oral presentation and 30 days for a journal submission). The Sponsor will review the communications for accuracy (thus avoiding potential discrepancies with submissions to health authorities), verify that confidential information is not being inadvertently divulged and provide any relevant supplementary information.

The Investigator may be required to sign the clinical study report if it is to be used in a registration submission to the health authorities of some countries.

**17.0 APPENDICES**

**Appendix 1: Schedule of Assessments**

**Appendix 2: Cytochrome 3A4 Inhibitors**

**APPENDIX 1: SCHEDULE OF ASSESSMENTS**

Study Procedures	Screening Days -28 to -1	All Cycles a	End of Treatme nt c	Quarterly Follow-up	
		Day 1 b			
Informed Consent	X				
a Cycle length is 21 days.
 
b Any procedures that were completed as part of the end-of-study visit for the original protocol that match those procedures required during Screening may be used and do not need to be repeated if they were performed within 7 days of Cycle 1 Day 1 of this extension study. For all subsequent cycles, Day 1 assessments may be performed up to 5 days before Day 1. For all cycles, safety assessments are required before each treatment cycle. All results must be available before dosing.
 
c End-of-treatment visit to occur 30 ± 7 days after last dose of NKTR-102.
 
d There will be a complete physical exam with height and weight during Screening, symptom-directed physical exams with weight during treatment, and a complete physical exam with weight at the End-of-Treatment. Vital signs include pulse, temperature, and blood pressure. ECOG performance status will be assessed as part of the physical exam.
 
e Radiological exams or digital photography required during Screening unless subjects had disease assessment within 8 weeks prior to Cycle 1 Day 1 dosing. Disease assessments will occur during the study as per local standard of care (e.g., approximately every 6-12 weeks). CT or MRI scanning is acceptable for radiologic exams.
 
f If Grade 3 or 4 neutropenia is observed, more frequent CBC with differentials are recommended until Grade 1 or less.
 
g Minimally required: hemoglobin, ANC, platelets, and creatinine. Other tests obtained according to the Investigator’s discretion.
 
h Body surface area (BSA) will be determined before the start of each cycle, based on baseline height and most recent weight. Body surface area may be calculated based on institutional guidelines.

Eligibility Criteria	X				
Physical Examination, Vital Signs d	X	X	X		
ECOG Performance Status d	X	X	X		
Serum Pregnancy Test (for WCBP)	X				
Urine Pregnancy Test (for WCBP)		X	X		
Disease Assessment per standard of care e	X	[X]			
CBC f, g	X	X			
Serum Chemistry g	X	X			
Body Surface Area (BSA) h		X			
NKTR-102 Infusion i		X			
Concomitant Medications j	X	X	X		
Adverse Events	X	X	X		
Survival Follow-up k				X	

**APPENDIX 1: SCHEDULE OF ASSESSMENTS**

Study Procedures	Screening Days -28 to -1	All Cycles a	End of Treatme nt c	Quarterly Follow-up	
		Day 1 b			
					i
					j
					k

i NKTR-102 dosing administration for Cycle 2+ may occur within ±4 days of the scheduled date.

j All concomitant medications, including over-the-counter medications, herbal therapies, dietary supplements, and St. John’s Wort.

k Approximately every 12 weeks (±4 weeks) following the End-of-Treatment visit, subjects will be contacted or have their medical records reviewed to assess disease status, survival status, receipt of subsequent anti-cancer therapy, and resolution of all toxicity attributable to study drug. Disease status during follow-up will only be assessed if the subject has not demonstrated disease progression since receiving NKTR-102. Quarterly follow-up will continue until death, withdrawal of consent by subject, physician decision, lost to follow-up, or the study is terminated by the Sponsor.

**APPENDIX 2: CYTOCHROME P450 3A INHIBITORS AND INDUCERS**

Strong CYP3A Inhibitors	Boceprevir, clarithromycin, conivaptan, grapefruit juice a , indinavir, itraconazole, ketoconazole, lopinavir/ritonavir, mibefradil b , nefazodone, nelfinavir, posaconazole, ritonavir, saquinavir, telaprevir, telithromycin, voriconazole
Moderate CYP3A Inhibitors	Amprenavir, aprepitant, atazanavir, ciprofloxacin, darunavir/ritonavir, diltiazem, erythromycin, fluconazole, fosamprenavir, grapefruit juice a , imatinib, verapamil
Weak CYP3A Inhibitors	Alprazolam, amiodarone, amlodipine, atorvastatin, bicalutamide, cilostazol, cimetidine, cyclosporine, fluoxetine, fluvoxamine, ginkgo c , goldenseal e , isoniazid, nilotinib, ranitidine, ranolazine, tipranavir/ritonavir, zileuton
Strong CYP3A Inducers	Avasimibe d , carbamazepine, phenytoin, rifampin, St. John's Wort e
Moderate CYP3A Inducers	Bosentan, efavirenz, etravirine, modafinil, nafcillin, phenobarbital

Please note the following: This is not an exhaustive list and is based on Food and Drug Administration (FDA) Guidance for Industry (Draft): Drug Interaction Studies - Study Design, Data Analysis, Implications for Dosing, and Labeling Recommendations, February 2012 (FDA Guidance for Industry, 2012) and Scripture C and Figg W, 2006. For the most current information, see the following links: <http://www.fda.gov/Drugs/DevelopmentApprovalProcess/DevelopmentResources/DrugInteractionsLabeling/ucm080499.htm> and <http://medicine.iupui.edu/clinpharm/ddis/table.aspx>.

- a The effect of grapefruit juice varies widely among brands and is concentration-, dose-, and preparation-dependent. Studies have shown that it can be classified as a “strong CYP3A inhibitor” when a certain preparation was used (e.g., high dose, double strength) or as a “moderate CYP3A inhibitor” when another preparation was used (e.g., low dose, single strength).
- b Withdrawn from the United States market because of safety reasons.
- c Herbal product.
- d Not a marketed drug.
- e The effect of St. John's Wort varies widely and is preparation-dependent.

Attachment 1: Table and Listing shells21

1.0 LIST OF ABBREVIATIONS

Abbreviation or Term	Definition/Explanation
AE	adverse event
ALT	alanine aminotransferase
AST	aspartate aminotransferase
AUC	area under the curve
BOR	Best Overall Response
BSA	body surface area
C _{max}	maximum concentration
CBC	complete blood count
CFR	Code of Federal Regulations
CPT-11	20-(S)-camptothecin
CRF	Case Report Form
CT	computed tomography
CYP3A4	cytochrome P450 3A4
D5W	dextrose for injection, 5 w/w%
ECG	electrocardiogram
EMA	European Medicines Agency
FDA	Food and Drug Administration
GCP	Good Clinical Practice
IB	Investigator's Brochure
ICF	informed consent form
ICH	International Conference on Harmonization
IEC	Independent Ethics Committee
IND	Investigational New Drug
IRB	Institutional Review Board
IV	intravenous
Kg	Kilogram
µg	Microgram
m ²	meters squared

mg	Milligram
mL	Milliliter
MedDRA	Medical Dictionary for Regulatory Activities
MRI	magnetic resonance imaging
MTD	maximum tolerated dose
NCI-CTCAE	National Cancer Institute-Common Terminology Criteria for Adverse Events
OTC	over-the-counter
PD	Progressive disease
PEG	polyethylene glycol
PK	pharmacokinetic
q14d	once every 14 days
q21d	once every 21 days
RECIST	Response Evaluation Criteria in Solid Tumors
RP2D	recommended phase 2 dose
SAE	Serious Adverse Event
SN38	7-ethyl-10-hydroxy-camptothecin
SUSAR	suspected unexpected serious adverse reactions
T _{1/2}	terminal elimination phase half-life
ULN	upper limit of normal
UGT1A1	uridine diphosphate-glucuronosyl transferase 1A1
US	United States
USP	United States Pharmacopeia
w×3 q4week	weekly for 3 weeks every 4 weeks
WBC	White Blood Cell

2.0 INTRODUCTION

This document describes of the planned statistical analyses of the data captured according to Nektar Therapeutics protocol 11-PIR-09 “An Open-Label, Multicenter, Extension Study of NKTR-102 in Subjects Previously Enrolled in NKTR-102 Studies” amendment version 2.0 dated 25 September 2013.

This study is conducted in accordance with the protocol, Good Clinical Practice (GCP), and all applicable regulatory requirements.

3.0 OBJECTIVES

3.1 Primary Objective

The primary objective of this study is to provide access to NKTR-102 to subjects who previously received NKTR-102 in a clinical trial and are without signs of disease progression since receiving NKTR-102.

3.2 Secondary Objectives

The secondary objectives of this study are: (1) to evaluate the safety of continued exposure to NKTR-102; (2) to observe disease status and survival status in subjects receiving NKTR-102; (3) to evaluate the efficacy of NKTR-102 in subjects with advanced or metastatic solid tumors.

4.0 STUDY ENDPOINTS

4.1 Endpoint

- Incidence and duration of toxicities, with severity grading according to NCI-CTCAE v 4.0.
- Tumor response per Response Evaluation Criteria in Solid Tumors (RECIST) version 1.1.

5.0 OVERALL STUDY DESIGN AND PLAN

5.1 Study Design

[figure not shown]
This is a multicenter, open-label, Phase 2 study of NKTR-102 in subjects with solid tumors who received NKTR-102 in a prior Nektar-sponsored clinical study. Following completion of NKTR-102 treatment on a prior NKTR-102 clinical study, subjects will be assessed for eligibility. The Sponsor must approve enrollment of all subjects.

Eligible subjects will continue treatment with NKTR-102 at a dose of 145 mg/m² or less in a q21d schedule as outlined in Figure 1: Study Schematic. Subjects who previously received a dose of NKTR-102 at <145 mg/m² will continue at the lower dose in this study. Subjects who underwent dose reduction of NKTR-102 due to observed toxicity prior to participation in the Extension study (Protocol 11-PIR-09) will not be re-escalated to the previous dose level upon resolution of the toxicity. Dose escalation for NKTR-102 is not permitted.

NKTR-102 will be administered as an IV infusion over approximately 90 minutes (± 15 minutes) on Day 1 of each 21-day treatment cycle.

Subjects will continue to receive repeated cycles of NKTR-102 treatment until disease progression, unacceptable toxicity, death, withdrawal of consent by the subject, Principal Investigator decision, subject non-compliance, lost to follow-up, or study is terminated by the Sponsor. After discontinuation of NKTR-102, all subjects, except those who withdraw consent from further study follow-up, are to be followed for disease status (as applicable), subsequent anti-cancer therapy, survival status, and resolution of toxicity attributable to study drug (with contact by phone, through a clinic visit, or through review of medical records at least every 3 months) until death.

Figure 1: Study Schematic

a Pre-treatment safety assessments and NKTR-102 administration will occur on Day 1 of each cycle.

b Tumor assessments will be performed as required by standard of care.

c Treatment cycles will be repeated until disease progression, unacceptable toxicity, death, withdrawal of consent by the subject, Principal Investigator decision, lost to follow-up, or study is terminated by Sponsor (See Section 5.1).

5.2 Study Medication and Treatment Assignment

Body surface area (BSA) will be determined before the start of each cycle, based on baseline height and current weight. NKTR-102 will be administered as an IV infusion over 90 minutes (\pm 15 minutes). The recommended dose and schedule of NKTR-102 is 145 mg/m² q21d, with BSA capped at 2.4 m². Body surface area is to be calculated based on institutional guidelines. Subjects who were previously receiving the 145 mg/m² dose will continue to receive it in this extension study in a q21d schedule.

Subjects originally enrolled in a clinical study in which a lower-than-recommended dose was administered (e.g., Protocol 12-102-13 in subjects with impaired liver function) or was being administered after a dose reduction will continue to receive that dose in a q21d schedule in this study if \geq 70 mg/m². For Protocol 12-102-13, the subjects with mild and moderate hepatic dysfunction, as defined in that study, will continue in this study (Protocol 11-PIR-09) to receive originally assigned doses of either 120 mg/m² (mild hepatic dysfunction) or 95 mg/m² (moderate hepatic dysfunction) in a q21d schedule.

Subjects originally enrolled in a clinical study in which a higher-than-recommended dose was being administered (e.g., Protocol 12-102-12 to explore the effects of NKTR-102 on cardiac function) will receive the recommended dose of NKTR-102 of 145 mg/m² in a q21d schedule in this study (Protocol 11-PIR-09).

Subjects who underwent dose reduction of NKTR-102 due to observed toxicity prior to participation in the Extension study [Protocol 11-PIR-09] will not be re-escalated to the previous dose level upon resolution of the toxicity. Dose escalation for NKTR-102 is not permitted.

6.0 STATISTICAL CONSIDERATIONS

6.1 General Considerations

Summary statistics for continuous variables will include the mean, standard deviation, median, and range (minimum and maximum). The mean and median will be presented to one decimal place beyond which the data were captured. The standard deviation will be presented to two decimal places beyond which the data were captured. The minimum and maximum will be presented to the precision with which the data were captured.

Categorical variables will be presented as frequency counts and percentages. A row or column denoted 'Missing' will be included in count tabulations where necessary to account for dropouts and missing values. Percentages will be rounded to 1 decimal place and the percent will be suppressed when the count is zero. The denominator will be the number of patients in that dose schedule within the population of interest unless otherwise noted.

All analyses will be summarized for all patients (Total) and by dose level if sample size allows. Data listings will be created to support each table and to present all data. Data listings will be presented by subject number (combination of original NKTR-102 study ID, subject and site ID).

Neither hypothesis testing nor a specific sample size is required for this study.

We will use the term "Original NKTR-102" when referencing the study where a subject first exposed to NKTR102 before rolling over to current study, "Current" to indicate 11-PIR-09 (extension) study and "Overall" to indicate information inclusive of the original NKTR-102 and current throughout this document. The default implication is "Current", when no study specific information is specified,.

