### 5.1 Inclusion Criteria

Each subject must meet the following criteria to be eligible for enrollment.

1. Subject or subject's legal representative must provide written informed consent.
2. Subject is able and willing to comply with the study visit schedule and procedures.
3. Subjects must have received prior treatment with NKTR-102 in a Nektar-sponsored study.
4. Subjects must be without signs of disease progression since receiving NKTR-102.
5. Women of childbearing potential must have a negative serum pregnancy test at screening and a negative urine pregnancy test at the predose visit of each cycle.
6. Women of childbearing potential and men who agree to use adequate contraception during study participation (at least two methods of contraception, one of which includes a barrier method [male condom] by the male partner or abstinence) or a male who has undergone a vasectomy greater than 6 months prior to Cycle 1 Day 1. Appropriate contraception must be used for at least 8 months after the last dose of the study drug on this extension study.
7. Subjects must meet requirements with respect to hematopoietic function (hemoglobin  $\geq 8.0$  g/dL or 80 g/L; absolute neutrophil count (ANC)  $\geq 1.5 \times 10^9$ /L; platelets  $\geq 75 \times 10^9$ /L).
8. Subjects must be able to receive the first dose of NKTR-102 in the extension study within 8 weeks after receiving their last dose of NKTR-102.

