Dose reductions may also be implemented for subjects who experience recurrent or specific severe toxicities (see [Table 4](#)). NKTR-102 doses for an individual subject may be reduced by 25 mg/m^2 based on conditions listed in [Table 4](#). Subjects should be discontinued from the study treatment if toxicity would indicate more than 2 dose reductions. Dose re-escalation for NKTR-102 is not permitted.

- For subjects entering this study at a starting dose of 145 mg/m^2: dose reductions to 120 mg/m^2, then to 95 mg/m^2 may occur based on conditions listed in [Table 4](#).
- For subjects (i.e., from Protocol 12-102-13) entering this study at a starting dose of 120 mg/m^2: dose reductions to 95 mg/m^2, then to 70 mg/m^2 may occur based on conditions listed in [Table 4](#).
- For subjects (i.e., from Protocol 12-102-13) entering this study at a starting dose of 95 mg/m^2: dose reduction to 70 mg/m^2 may occur based on conditions listed in [Table 4](#).
- For subjects (i.e., from Protocol 12-102-13) entering this study at a starting dose of 50 mg/m^2: dose reduction should be approved by Medical Monitor.
- [Table 4](#) provides instructions regarding dose modification.
- DURING A CYCLE: [Table 4](#)/Column 2 describes the recommended guidelines for management and supportive care during a cycle of therapy.
- INITIATION OF A SUBSEQUENT CYCLE: [Table 4](#)/Column 3 describes the recommended dose modifications for Day 1 in subsequent cycles of therapy. All dose modifications in a new cycle should be based on the worst toxicity observed in the previous cycle and the dose reduction will be relative to the Day 1 dose of the previous cycle.

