7.0 STATISTICAL ANALYSIS

7.1 Patient Disposition

A summary of patient disposition will display the number of patients by original NKTR-102 study entered and by dose level received in this study. The number of enrolled, discontinued from the treatment and exited the study and reasons for discontinuation will be tabulated. Disposition data will be presented in a data listing.

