7.6 Efficacy Analysis

Tumor response will be assessed by the investigator according to the frequency that patient's standard of care allows. Baseline will be the assessment at screening visit. Data on the best response and disease progression (per physician assessment) will be collected according to RECIST criteria version 1.1 (Eisenhauser et al., 2009). Tumor assessment and responses at the baseline and subsequent visit will be presented in a listing. Best overall response (BOR) by investigator assessment will be summarized. Time to progression and survival time will be calculated from first dose of original NKTR-102 study enrollment. Time to progression is defined as time from date of first dose of original NKTR-012 study to the 1st date of progressive disease (PD) per investigator assessment in current study. Patients without PD will be censored in last visit/follow-up date. Time to death is defined as time from date of first dose of original NKTR-102 study to death date. Patients without death date will be censored in last visit/follow-up date.

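### By-dose displays of TTP and survival are not exempted from SAP 6.1, although toxicity reductions after the time origin can decide a subject's dose level

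*SAP*

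**What the plan says.** **Breakdown.** SAP 6.1 states: "All analyses will be summarized for all patients (Total) and by dose level if sample size allows". It does not define dose level. SAP 7.1 tabulates disposition "by original NKTR-102 study entered and by dose level received in this study", while SAP 6.3 uses the initial planned dose (145, 120 or 95 mg/m²) for expected dose intensity.

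**Clock.** SAP 7.6: "Time to progression and survival time will be calculated from first dose of original NKTR-102 study enrollment". TTP runs "to the 1st date of progressive disease (PD) per investigator assessment in current study". For survival, "Time to death is defined as time from date of first dose of original NKTR-102 study to death date". There is no landmark, delayed entry or time-varying dose, and no exception to 6.1.

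**How dose level arises.** SAP 5.2 carries earlier reductions forward: subjects for whom a lower dose "was being administered after a dose reduction will continue to receive that dose in a q21d schedule in this study", subject to a dose floor that does not affect this point. Protocol 6.7 allows further reductions during the extension: "All dose modifications in a new cycle should be based on the worst toxicity observed in the previous cycle". Re-escalation is barred. Separately, subjects from hepatic study 12-102-13 hold 120 or 95 mg/m² by assignment.

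**Entry.** Protocol 5.1: "Subjects must be without signs of disease progression since receiving NKTR-102". Every dose group therefore enters with some progression-free time already accrued.

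**The concern.** A subject who started at 145 mg/m² reaches a lower level only by staying on drug, progression-free, until a toxicity triggers a reduction. The TTP and survival clock has been running since the original first dose. Group membership is thus decided after time zero, and reduced subjects are guaranteed at least the time it took to be reduced. This is immortal-time bias between columns. It is separate from the upward shift in the Total column that comes from admitting only progression-free subjects.

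Evaluating efficacy is a secondary objective (SAP 3.2). A by-dose table built to the 6.1 default could suggest that lower doses give longer disease control when dose has no effect.

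**Working it through.** The plan states no sample size, power or event count for these endpoints, so there is no figure to reproduce. The check simulates the null: dose has no effect on outcome.

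**Inputs from the documents**
- Median TTP 4.7 months: median PFS in the Phase 2 breast cancer study, both schedules combined (Protocol 2.1.2.2). 4.7 × 30.44 = 143.1 days.
- Median time to reduction 120 days: BEACON onset of Grade ≥3 neutropenia (Protocol 2.1.2.5), used as a proxy.

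**Assumptions not in the documents**
- TTP (T) is exponential; there is no censoring.
- Rollover (E) is uniform over days 42–365 after the original first dose.
- 40% of subjects are prone to reduction; their reduction time (R) is exponential and independent of T.

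**Method.** Keep subjects with T > E. Reduced by entry dose means R < E. Reduced by lowest dose received means R < T.

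| Grouping | Clock starts | Rollover | Median TTP, reduced vs full (days) |
|---|---|---|---|
| Entry dose | Original first dose | Days 42–365 | 354 vs 313 |
| Lowest dose received | Original first dose | Days 42–365 | 360 vs 305 |
| Entry dose | Original first dose | Fixed, day 122 | 265 vs 265 |
| Lowest dose received | Original first dose | Fixed, day 122 | 301 vs 250 |
| Lowest dose received | Extension Cycle 1 Day 1 | Days 42–365 | 173 vs 130 |
| Entry dose | Extension Cycle 1 Day 1 | Days 42–365 | 143 vs 143 |

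Monte Carlo error is about a day.

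**Why entry dose depends on rollover.** With exponential T, the remaining time T − E has median 143 days whatever E is. With rollover fixed at day 122, both groups have median 122 + 143 = 265. When E varies, subjects already reduced at entry tend to be those who rolled over later, and that difference in E is the whole gap.

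**Range.** Over 27 settings (25%, 40% or 100% prone; median reduction 40, 120 or 365 days; rollover over days 42–180, 42–365 or 21–730) the false advantage was about 7 to 172 days by entry dose and 9 to 271 days by lowest dose received. All three rollover ranges vary, so this range excludes the zero seen with fixed rollover.

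**A second set of assumptions.** Here all subjects are prone, the median time to reduction is 6 months, rollover is uniform over 1–12 months, and OS is calibrated to the documented 10.3-month median.
- TTP, reduced vs full: 11.7 vs 9.2 months by entry dose; 12.2 vs 7.0 by lowest dose received.
- OS: 16.9 vs 14.7 and 17.5 vs 12.2 months respectively.
- With 150 subjects (the enrolment cap), the reduced group had the longer median TTP in 97% of null trials by entry dose and 100% by lowest dose received. With rollover at about 4 months for everyone, the entry-dose figure was 48%, which is chance.

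**Hepatic-study subjects.** When they made up 57%, 48% or 40% of the low-dose entry group, with assumed hazard ratios of 1.0, 1.5 and 2.0, low-dose vs full-dose medians were 11.0 vs 9.3, 9.9 vs 9.3 and 9.4 vs 9.3 months.

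**The case against.** The strongest reply is that the plan does not name the table at issue. SAP 6.1 is a general default, limited by sample size. SAP 7.6 says TTP and survival will be calculated and names no by-dose output. Protocol 12.2 asks for dose level only for adverse events, and for tumor response by histology. The SAP's table shells, listed as Attachment 1, are not in the text available here and may define the columns. The use of initial planned dose in SAP 6.3 also points towards one entry-dose column per subject. All this makes the display uncertain, but none of it exempts these endpoints from the default.

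Some stronger readings are tempting and are not supported:
- *The bias arises however dose level is defined.* By entry dose it disappears when rollover time is common to all subjects, and the documents give no rollover distribution. Some spread is plausible because subjects come from several original studies.
- *Only reduced subjects carry guaranteed time.* All must be progression-free at entry; only the excess biases the comparison.
- *Low dose always means toxicity.* Hepatic-study subjects were assigned theirs and could shrink the gap towards zero.
- *About a quarter of 145 mg/m² starters would fall in two columns.* BEACON's Grade ≥2 diarrhea rate is 14.8% + 9.6% = 24.4%, but it covers the whole of treatment, and Protocol 6.8 puts median onset at 40 days, so many reductions would precede rollover. The illustration gives about 12% of full-dose entrants reduced in the extension.
- *Best overall response is biased too.* The calculations do not show this.

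**Conclusion.** The concern holds in a conditional form. The plan permits by-dose displays of TTP and survival in which toxicity reductions after the time origin decide the column. With columns by dose received in the extension, reduced doses looked better in every null scenario run. With columns by entry dose, this happens only when rollover time varies. The illustrated gap is 354 − 313 = 41 days by entry dose and 360 − 305 = 55 days by lowest dose received. These sizes rest on the assumed reduction and rollover times and on exponential TTP without hepatic-study subjects, so they show direction and plausible scale and are not forecasts.

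A reader might infer an inflated type I error. SAP 6.1 plans no hypothesis testing, so the harm is a misleading descriptive summary. It still merits correction, because the summary would serve the efficacy objective and the repair is nearly free.

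**What to change.** Add to SAP 7.6: *As an exception to Section 6.1, TTP and survival measured from the first dose of the original study are presented for Total only.*

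If a by-dose display is kept:
- group by the dose level at extension Cycle 1 Day 1, unchanged by later reductions, and count time from that date; moving the clock alone is not enough (173 vs 130 days);
- show hepatic-study subjects separately;
- label it descriptive. If prognosis varies between subjects a gap can remain: 13.4 vs 11.1 months with gamma frailty of variance 1 and rollover over 1–12 months. Delayed entry, or adjustment for time since the original first dose, may then also be needed.

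Leave the adverse-event summaries by dose level in Protocol 12.2 unchanged. Forcing entry-dose columns on every table would credit events after a reduction to the starting dose.

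Cost: one SAP sentence, or a short paragraph if the by-dose display is kept, and no new data. By-dose TTP and survival from the original first dose would no longer be shown.
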